## **9.0 DATA ANALYSIS**

Data Analysis will be performed by [name] at the Institute for Minority Health Research at the University of Illinois Chicago and [name].

## **10.0/11.0        QUALITY CONTROL AND QUALITY ASSURANCE & DATA AND SAFETY MONITORING**

The research project is a two-arm randomized clinical trial that includes a single site. This is an uncomplicated, blinded trial, and the risk is considered to be minimal. The University of Illinois at Chicago (UIC) Institutional Review Board (IRB) will review and approve the research before the research is conducted and an IRB-approved data and safety monitoring plan will be documented. Due to the vulnerable study population and the immediate public health impact, a Data Safety and Monitoring Board (DSMB) will be assembled to ensure the safety of the subjects and the validity and integrity of the data generated.

Therefore, the PI and the PI's research team have primary responsibility for monitoring subject safety. The PI is responsible for minimizing research-associated risk. This is done through continuous monitoring of the procedures and through weekly research team meetings. Three senior individuals with expertise in hypertension and clinical trials, external to the research team will serve on the DSMB. [name], in consultation with the DSMB, will report any adverse events to the Funding Institute and Center. We will attempt to determine the cause of the adverse event and make a determination as to whether the adverse event was related to any study-related activity. When appropriate, we will make changes to the informed consent document and/or study protocol resulting from an adverse event. The following is a list of Adverse Event descriptors that will serve as a guideline to notify IRB and DSMB review boards in the event any TOUCHED study participants experience abnormal symptoms or conditions.

**Table 2: Adverse events descriptors**

Study Related Adverse Events	
Symptoms or Condition	Expanded Comments on Symptom or Condition
Rash/itching	Covers rash, itching, hives, flushing or similar change in skin. Do not report if symptoms are related to contact with an allergen such as poison ivy or oak.
Angioedema	Covers swelling of the lips, face or tongue.
Cough	Use only for a new cough that is not related to a cold, other infection or seasonal allergy and that follows initiation of a new medication.
Lower extremity edema	Swollen legs or lower extremity edema that is new in onset or substantially worse than usual for the subject.
Lightheadedness or passing out	Lightheadedness, dizziness, passing out, or loss of consciousness
Orthostatic hypotension	Orthostatic hypotension (that is not chronic)

Hypertensive urgency	As indicated by the average blood pressure found at a study visit or a single BP found during a clinic visit that occurred since the last study visit
Non-study Related Adverse Events	
Symptoms or Condition	Expanded Comments on Symptom or Condition
Fever	Do not report if fever is related to a cold or viral infection.
Rhythm disorder	Covers any new rhythm disorder such as tachycardia or a racing heartbeat that is not typical for the subject.
Chest pain	Covers any new development or worsening of chest pain that does not reflect stable angina.
Headache	Do not report if subject has a history of frequent headaches.
Other pain	Other pain that is not related to an injury or chronic condition.
Shortness of breath	Covers shortness of breath, wheezes, stridor, and gasping for breath that is not typical for the subject.
Weight gain	Use for new and unintended weight gain with sudden onset, e.g., related to CHF.
Kidney problem	Covers a new or worsening kidney problem such as acute renal failure or a 20% increase in creatinine level; do not report a kidney infection.
Liver problem	Covers a new or worsening liver problem such as an increase in one or more liver function tests to > 2 times normal.
Nausea or vomiting	Do not report instances related to influenza, other infection or food poisoning.
Other GI problem	Use only for a new GI problem such as diarrhea, constipation, cramping or abdominal pain that is not related to influenza, other infection or food poisoning; do not use to report nausea or vomiting
Neurological change	Use only for a new or worsening neurological change, such as tingling in hands or feet
Trouble walking or falls	Trouble walking or falls
Urinary problem	Urinary problem such as urgency or frequency that is not related to infection
Blood disorder	Bleeding that is not related to or a blood dyscrasia such as leucopenia or thrombocytopenia
Change in lab values	Change in lab values related to a drug side effect such as a marked drop in potassium or sodium or a marked increase in serum creatinine.
Weakness	Covers new onset or worsening of weakness, fatigue, lethargy or other marked decrease in strength
Other	CHECK WITH [name] BEFORE USING THE 'Other' DESCRIPTOR

*In the event the "Other" descriptor is to be used to report a specific symptom that is not on the list above the Principal Investigator, [name], must be consulted.*

The PI is also responsible for protecting the confidentiality of subjects' data. All documents and information about this study will be kept confidential in accordance with federal, state, and local laws and regulations. Medical records and data generated by the study may be reviewed by the UIC Institutional Review Board, the Office for Human Research Protections, and the National Institutes of Health to assure proper conduct of the study and compliance with federal regulations. The results of this study will be published. If results are published, no subject will be identified by name.

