#### **Details of ED Screening (risk assessment, both arms)**

**BP Measurement:** Prior to randomization all participants will be screened using a standardized 5- point pain scale with 5 indicating severe pain and 0 no pain. Participants with moderate to severe pain (3-5) will not be randomized until their pain scale is improved (0-2). Participants will then have a standard BP measurement taken (as per AHA guidelines) to ensure consistency and standardization of BP measurements throughout the trial.

The blood pressure measurements will be obtained using standard monitors currently available in our Emergency Department: Welch Allyn, Model VSM 6000 series, Configuration Number: NIBP, Pulse Rate, SPO2, Temp, Hardware Version P3, Software Version 1.71.03.

The blood pressure measurement protocol based on the AHA guidelines are as follow:

1. The patient will be asked to remove all clothing that covers the location of cuff placement.

2. The individual will be comfortably seated, with the legs uncrossed, and the back and arm supported, such that the middle of the cuff on the upper arm is at the level of the right atrium (the mid-point of the sternum).
3. The patient will be instructed to relax as much as possible and to not talk during the measurement procedure. The patient will be asked to sit quietly for 5 minutes before the first reading is taken.
4. A minimum of three readings will be taken and the average of the last two readings will be used to record the measurement. There will be intervals of at least 1 minute between readings.
5. If there is >4 mm Hg difference between the second and third readings, additional (one or two) readings will be obtained and then the average of the two closest readings will be used.

***Atherosclerotic Cardiovascular Disease (ASCVD) Risk Score:*** Using ASCVD Risk Score calculators preloaded on study iPads, participants will have their risk score calculated by entering their age, tobacco status (Y/N), Systolic BP, Cholesterol/HDL, and BP treatment (Y/N). Point of care cholesterol/HDL measurement will be obtained using the Polymer Technology Systems CardioChek PA Analyzer, which analyzes up to 4 cholesterol types with a single fingerstick of blood and is CLIA-waived and FDA approved.

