patient slips on the cuff and turns on the monitor to measure his/her BP. All BP readings automatically sync with the app, which creates an easy-to-understand chart of all the measurements and provides participants with instant color-coded feedback based on AHA recommendations for hypertension. Synced data are automatically uploaded from the mobile app to the iCardia server of our study. Participants will be shown how to use the BP monitor and app by RAs, view a standardized 2-minute instructional video and asked to confirm/demonstrate that they understood how to use the device and app using the teach-back method prior to leaving the ED. Participants will be asked to check their BP at home daily and use the mobile app to view their data. The EMT's will set-up daily automatic reminders in each participant's mobile app that will prompt them to measure their BP at a preferred time. In case of missed measurements for three consecutive days, participants will receive one text-message per day through the iCardia platform for four consecutive days until they complete a BP measurement. In case of missed measurements for 7 consecutive days, participants will be contacted by phone by the RA's. Participants will also receive 3 behavioral text messages per week that are aimed at improving medication adherence and BP measurement adherence. All data will be remotely monitored by the RA's through the iCardia platform. Participants will be informed that the Health Mate app is not a telemonitoring app and in the event the participant is experiencing a hypertensive crisis ( $>180/120$ ) they must contact a physician immediately. The patient-centered benefit of home BP monitoring has been repeatedly shown and is recommended as an important component of HTN management. Home BP monitoring has been shown to improve adherence to medications, induce healthy lifestyle changes, and aid in optimizing of treatment. In addition, use of the home BP monitoring values will serve as a safety feature to avoid pushing BP too low in study participants.

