0.45	5.40	9.45	156	209	178
0.50	6.00	10.5	126	169	144
*Effect size is defined as difference in means divided by standard deviation. From our pilot study: DBP Standard deviation 12 mmHg; SBP Standard Deviation 21 mmHg.					
**25% attrition is assumed and thus required sample size, N**, is obtained by dividing calculated sample size, N, by 0.75.					

*Sample Size:* The primary hypothesis of the study is that the difference in systolic blood pressure from baseline to month 6 is different across the two treatment arms. Testing this hypothesis amounts to testing difference in mean systolic blood pressure between the two treatment groups at 6 months, due to randomization (since the mean SBP at baseline is the same across groups). Thus, sample size estimation is determined by comparing

the mean SBP at 6 months using a two-sample, two-sided, 5% significance t-test with 80% and

85% statistical power. Sample size is calculated first to detect a pre-determined effect size (difference in means divided by standard deviation) and then converted to blood pressure units, namely mmHg. Data from our pilot study resulted in estimates of DBP standard deviation of 12 mmHg and SBP standard deviation of 21 mmHg. For example, the required sample size to detect an effect size of 0.25 ( $0.25*12 = 3$  mmHg in DBP, and  $0.25*21 = 5.25$  mmHg in SBP) is 504 for 80% power and 576 for 85% power, using a two-sided, two-sample 5% significance t-test. An attrition-adjustment to the calculated sample size give 673 and 770 patients for 80% and 85%, respectively.

*The statistical analysis:* Mean BPs will be compared across groups using a two-sample, two-sided, 5% significance t-test. The analysis will be then extended to gain statistical power by adjusting the comparison by baseline BP levels. An intention-to-treat analysis will be undertaken by using mixed effects models so that all the available information on each patient is used for the analyses. Further analyses using maximum likelihood estimators for data imputation and weighting will be implemented to better account for missing data. Moreover, key variables (age, sex, race/ethnicity) will be compared across treatment groups and if different will be used in a multivariate mixed effects model.

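### A study-visit blood pressure becomes an adverse event only when it is high, so symptom-free over-lowering is not counted by arm and adds to the apparent effect

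*Combined protocol and SAP*

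**What the plan says.** **High readings.** In section 10.0/11.0, Table 2, hypertensive urgency is identified "As indicated by the average blood pressure found at a study visit or a single BP found during a clinic visit that occurred since the" (previous study visit). No symptom is required. The row gives no mmHg limit.

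**Low readings.** No row refers to a low measured BP. The low-BP diagnosis listed is "Orthostatic hypotension (that is not chronic"), with no source or method. Symptoms that low BP could cause are listed: "Lightheadedness, dizziness, passing out, or loss of consciousness" among the study-related events, and "Trouble walking or falls" and weakness among the non-study-related ones. The PI must be consulted when the Other "descriptor is to be used to report a specific symptom that is not on the list above".

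**How BP is measured.** Section 6.0, Details of ED Screening, requires that "The individual will be comfortably seated, with the legs uncrossed, and the back and arm supported". The follow-up visits use study protocols and AHA guidelines. No standing reading is described anywhere.

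**The stated risk.** Section 6.0, Details of Intervention Components, says that "use of the home BP monitoring values will serve as a safety feature to avoid pushing BP too low in study participants". The general description of arm 2 in section 6.0 says the same. Home monitors go to arm 2 only. The PACHT-c paragraph lets the provider start antihypertensive drugs at the consultation.

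**The analysis.** Section 12.0 says "Mean BPs will be compared across groups using a two-sample, two-sided, 5% significance t-test", extended by linear and mixed-effects models for continuous BP. H1 in section 3.0 favours the larger fall. Section 12.0 plans no count of low readings and no adverse-event table.

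**The concern.** The plan names a harm that an effective BP intervention could cause, but gives no definition of it, no reporting rule and no table. A high study-visit average is an event whether or not the patient feels anything. A low average is not, unless something else brings it to notice.

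Home readings cannot fill the gap. They exist in one arm only, so they allow no comparison, and the text sets no low limit for them. For high readings it does: participants are told to contact a physician above 180/120.

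The efficacy analysis has no lower limit either. Any extra fall in arm 2, wanted or not, moves the mean difference in the favourable direction. A report could then show a clear fall in mean systolic BP (SBP) and be unable to say from its planned tables how many patients in each arm were taken too low. Readers of a BP-lowering trial usually ask for that number.

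**Working it through.** **1. High and low readings side by side**

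| | High BP | Low BP |
|---|---|---|
| Row based on measured study-visit BP | Yes (hypertensive urgency) | None |
| Symptoms needed | No | Yes, unless a diagnosis of orthostatic hypotension is reported or Other is used |
| Detectable by the described BP procedure | Yes (seated average) | A low seated average is recorded but has no row; orthostatic hypotension needs a change of posture, which is not measured |
| Limit given for home readings | 180/120 | None |
| By-arm count in section 12.0 | None | None |

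**2. The plan's own figures.** Inputs from section 12.0: SBP SD 21 mmHg, effect size 0.25 (0.25 × 21 = 5.25 mmHg), two-sided 5%. The total is N = 4(z₀.₉₇₅ + z_power)²/0.25².

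- 80% power: 4 × (1.960 + 0.842)²/0.0625 = 502.3, so 252 per arm, 504 in total.
- 85% power: 4 × (1.960 + 1.036)²/0.0625 = 574.6, so 288 per arm, 576 in total.

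Both match the plan. This point does not affect the sample size.

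**3. Effect on the mean.** If a share p of arm 2 is lowered by a further d mmHg, the arm difference grows by p × d. The values of p and d are assumed.

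- 2% × 10 mmHg = 0.2 mmHg (0.2/5.25 = 4% of the target effect)
- 5% × 20 mmHg = 1.0 mmHg (19%)
- 10% × 30 mmHg = 3.0 mmHg (57%)

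**4. How many low readings to expect.** Assumptions: normal SBP, SD 21 in both arms, a pure shift of 5.25 mmHg, and 288 analysed per arm. The documents give no 6-month usual-care mean m, so it is varied. The cut c = 100 mmHg only shows scale and is not a proposed limit.

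Arm 1: p₁ = Φ((c − m)/21). Arm 2: p₂ = Φ((c − m + 5.25)/21). CI half-width = 1.96 × √[(p₁q₁ + p₂q₂)/288], where q = 1 − p.

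Worked case, m = 135: p₁ = Φ(−35/21) = Φ(−1.667) = 4.8%, and p₂ = Φ(−29.75/21) = Φ(−1.417) = 7.8%.

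| m | Arm 1 | Arm 2 | Patients per 288 | Difference (points) | 95% CI half-width (points) |
|---|---|---|---|---|---|
| 135 | 4.8% | 7.8% | 14 vs 23 | 3.0 | 4.0 |
| 140 | 2.8% | 4.9% | 8 vs 14 | 2.1 | 3.2 |
| 145 | 1.6% | 2.9% | 5 vs 8 | 1.3 | 2.4 |

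At c = 90 the counts fall to about 5 vs 8, 2 vs 5 and 1 vs 3.

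**The case against.** The best defence is that Table 2 is wider than its BP rows, and much of that defence stands.

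- **A reader might infer that low BP can be reported only as orthostatic hypotension.** The table does not support this. The row on lightheadedness and loss of consciousness is study-related and has no postural condition. Falls, weakness and Other are also available.
- **A reader might infer that orthostatic hypotension can never be recorded.** The documents show only that study readings cannot detect it. The row names no source, so a diagnosis from outside care or a participant's report could count.
- **A reader might infer that over-lowering is left out of safety.** Symptoms are captured and home values are called a safety feature. Section 10.0/11.0 calls the list a guideline and provides for weekly team review, an external DSMB and an IRB-approved monitoring plan that is not part of these documents.
- **A reader might infer that the safety record as a whole favours arm 2.** This is not shown. Rash, angioedema, cough, edema and lightheadedness are plausible drug effects, and their rows could count against arm 2.

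It is also fair to say that any mean endpoint lacks a floor, that the documents do not show a symptom-free low reading to be harmful, and that the visit readings are kept, so a count could be made later.

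The core survives. The plan does not tie over-lowering to symptoms when it names it. Other is worded for a symptom, and ad hoc entries give no consistent count by arm. A count made after results are known needs a cut-off chosen after results are known. Detection of orthostatic hypotension through outside care may also differ by arm, because the intervention aims to increase that care.

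**Conclusion.** The concern holds in a limited form. Table 2 treats a measured study-visit BP as an event on the high side only, although section 6.0 names over-lowering as a risk. The gap is symptom-free low seated BP: it is not counted by arm, and it adds to the mean difference.

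The structural finding rests on the text alone. Its size cannot be derived from the documents. The illustration, roughly 5 to 14 patients in usual care and 8 to 23 in arm 2 below 100 mmHg, depends on the assumed means, normality, equal SDs, pure shift and cut. It shows what a successful trial might produce, not an error in the plan's figures. In every scenario the CI half-width exceeds the expected difference, so the table would describe rather than test.

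The primary analysis and the sample size are unaffected. The change is worth making because it is cheap and because the cut-off loses credibility if it is chosen later.

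**What to change.** 1. Reconcile the over-lowering statements in section 6.0 with Table 2. Add a low-BP row based on the average seated BP at each study visit, applied identically in both arms. The investigators and the existing DSMB should set the cut-off before outcome data by arm are seen; none is proposed here.
2. In section 12.0, add a safety table giving by arm the number and proportion below that cut-off at months 3 and 6, out of those measured, with the risk difference and its 95% CI. Use study-visit BP only, because home readings exist in arm 2 alone.
3. State that no study procedure measures orthostatic hypotension, so that few or no reports are not read as evidence of safety.

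Cost: one row, one table and one sentence. Table 1 already schedules BP in both arms at months 3 and 6, so no visit or procedure is added. The drawback is small counts and a wide interval, which the report should acknowledge.

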The Usual Care group (Arm 1) will receive preprinted discharge instructions and an outpatient referral. This group represents standard of care. All other interventions in arm 2 are research activities.

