**PACHT-c:** All participants randomized to the E intervention will have a focused consultation with either a clinical pharmacist or an APN. To ensure consistency throughout the trial, the PACHT-c intervention will be standardized and interchangeable between the clinical pharmacists and APNs. During the day, the on-site ED clinical pharmacist will provide consultations. During evening and weekend hours, consultations will be provided by the APN located in the ED Clinical Decision Unit (CDU). The CDU is open 24 hours a day, 7 days a week. During this consultation, the pharmacist/APN repeats the BP measurement; reviews the screening

assessments; and reviews general principles of BP control including nutrition, exercise, and smoking cessation. BP will be managed according to the current published guidelines available regarding initiation of first-line antihypertensive medications. Patients with BP  $\geq 140/90$  mmHg may be started on antihypertensive medications by the provider during the consultation if appropriate. All PACTH-c clinic notes will be accessible in the EMR, which is shared between both the ED and our FQHC, Mile Square Health Center. No tests will be ordered during the pharmacy follow-up.

[figure not shown]
Based on our pilot trial (IRB Protocol # 2015-0323) the E intervention takes about 20-30 minutes following randomization. Once patients are identified for discharge, the wait time before physically leaving the ED provides ample time to consent and complete the initial assessments based on participant randomization at the bedside without adding delays. Participants will be approached for study participation after they have been identified for discharge and BEFORE being physically discharged from the ED.

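### Table 2 fixes relatedness by symptom name and places a drug-side-effect row under Non-study Related, although arm 2 may start antihypertensives at the study consultation; this conflicts with the event-by-event determination in section 10.0/11.0

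*Combined protocol and SAP*

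**What the plan says.** Section 10.0/11.0 introduces Table 2 as a guideline for notifying the IRB and the DSMB. The table has two blocks. The Study Related block has seven descriptors: rash/itching, angioedema, cough, lower extremity edema, lightheadedness or passing out, orthostatic hypotension, and hypertensive urgency. The second block is headed "Non-study Related Adverse Events" and runs to the end of the table with 18 descriptors, counting Other. Four of these matter here:

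- Lab values: "Change in lab values related to a drug side effect such as a marked drop in potassium or sodium"; the row goes on to name a marked rise in serum creatinine.
- Kidney: "Covers a new or worsening kidney problem such as acute renal failure or a 20% increase in creatinine level".
- Gait: "Trouble walking or falls".
- Weakness: "Covers new onset or worsening of weakness, fatigue, lethargy or other marked decrease in strength".

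The text before the table says that for an adverse event the team will try to establish the cause and "make a determination as to whether the adverse event was related to any study-related activity".

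In section 6.0, the PACHT-c paragraph under Details of Intervention Components says that patients at or above 140/90 mmHg "may be started on antihypertensive medications by the provider during the consultation if appropriate". Just before Table 1, after describing usual care as standard of care, section 6.0 states: "All other interventions in arm 2 are research activities".

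**The concern.** Relatedness is a judgement about one event in one patient. A heading over a list of symptoms makes that judgement in advance, for every patient. Here the heading points the wrong way for at least one row: a side effect of a drug started at the study consultation is, in the protocol's own terms, related to a research activity, yet it carries the non-study label.

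What is at stake is attribution. Someone completing a form from Table 2 meets a default of unrelated for electrolyte changes, renal events, falls and weakness. Any later summary restricted to related events, for instance one prepared for the DSMB, would then omit events that belong in it. Medication started at the study consultation occurs only in arm 2, so the omission would fall on that arm. Other text does little to offset this. The risk list in section 7.0 names no medication risk, and section 12.0 plans no tabulation of adverse events by arm that would show an imbalance whatever the labels.

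**Working it through.** No arithmetic applies beyond counting rows, because the documents give no expected event rate, no number expected to start a drug and no planned safety comparison. The check sets the texts against each other.

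**1. Row count.** Study Related: 7. Non-study Related: 12 from fever to neurological change, plus 6 from trouble walking to Other, giving 12 + 6 = 18. Total 7 + 18 = 25. No further heading appears between the second heading and the end of the table, so all 18 rows fall under it.

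**2. Is a drug started at the consultation a study activity?** Section 6.0 gives every arm 2 participant the PACHT-c consultation, permits antihypertensives to be started there, and classes what arm 2 receives beyond usual care as research. A side effect of such a drug is therefore related to a study activity by the protocol's own definitions.

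**3. Lab row against its heading.** The row attributes the change to a drug. The heading says the event is not related to the study. Both can be true of a drug the patient was already taking or was given elsewhere. They cannot both be true of a drug started at the consultation. One heading cannot separate these cases.

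**4. Lab row against the cough row.** In the Study Related block, cough counts only if it came after a new drug was begun. The table thus accepts a new drug as a study-related cause in one row and files an explicit drug effect as non-study in another.

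**5. Falls and weakness against lightheadedness.** Lightheadedness, passing out and orthostatic hypotension are Study Related. A fall is Non-study Related. An episode in which a patient becomes dizzy and falls could take either label, depending on the descriptor chosen.

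**6. Headings against the text of section 10.0/11.0.** The text promises a determination for each event. The headings supply an answer for each descriptor. No sentence says which governs when they differ.

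**7. Strength by row.** Only the lab row names a drug as the cause, so only there does the heading conflict with the row's own wording. The kidney, falls and weakness rows name no cause. They can be drug effects but need not be, and for them the fault is an unwarranted default.

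**The case against.** The strongest reply is that the text of section 10.0/11.0 already supplies the right rule. It requires a causality determination for each event, calls the table only a guideline, and offers the whole list, both blocks, for IRB and DSMB notification. It also says that any adverse events go to the funder. No sentence gives the second block a slower or lesser route. In addition, angioedema, edema, cough, lightheadedness and orthostatic hypotension are already under Study Related. The data and safety monitoring plan that the section mentions is not among the documents, so how the headings work on the form is unknown.

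Most of this stands and limits what can be claimed. Three stronger readings are tempting, and the documents support none of them:

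- A reader might infer that these harms will go unreported. The notification and reporting text covers both blocks.
- A reader might infer that a planned between-arm comparison of related events is biased. Section 12.0 contains no such comparison; the risk applies only to a summary that might be made later.
- A reader might infer that every event in these rows is misattributed, or that all 385 arm 2 participants are exposed. Many falls, kidney problems and episodes of weakness would be unrelated to the study, the list also covers the 385 usual-care participants, and medication is started only where the provider finds it appropriate.

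The reply does not remove the conflict itself. A document that both presets relatedness and promises to determine it needs to say which applies.

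**Conclusion.** The point holds as an internal contradiction in safety attribution. Table 2 labels relatedness in advance, and its Non-study Related block includes one row worded as a drug effect and three others (kidney problems, falls, weakness) that can be drug effects, while arm 2 may begin antihypertensives as part of a research activity. This is inconsistent with the lab row's own wording, with the cough row, and with the event-level determination in section 10.0/11.0.

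The consequence is a possible default mislabelling of some harms of study-started medication. Its size cannot be derived from the documents: 385 is the number planned to receive the consultation, not the number who start a drug, and the row counts describe the table rather than the number of events. The conclusion assumes that staff use the table with its headings as printed; if the operational form drops them, only the wording of the protocol needs repair. The correction is worth making because it is specific, costs very little and improves attribution.

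**What to change.** Delete the two relatedness headings and keep Table 2 as a single list of descriptors. State in section 10.0/11.0 that relatedness is recorded for each event whatever the descriptor, as its text already promises, and add to the adverse-event form a field for relation to any medication started at the study consultation. Add a sentence to section 12.0 that all adverse events will be summarised by arm regardless of attribution.

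The cost is one table edit, one form field and a descriptive table. No extra patients, visits or procedures are needed, and clinical management does not change.
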